	
 11. To use plasma proteomics to identify proteins whose expression is altered in the first 7 days of life in infants who later are diagnosed with BPD. 12. To use plasma proteomics to identify expression pathways associated with specific preterm respiratory endotypes in samples obtained at 72 hours and 7 days post-birth. 13. To determine the impact of clinical interventions on the development of the respiratory phenotype.
OUTCOMES AND OUTCOME MEASURES	
The primary outcome is identification of functional endotypes defined from clinical, plasma protein and lung imaging measures using cross-sectional and longitudinal latent class analysis.
 
The secondary outcomes include the functional endotype at 72 hours, the relationship between early life phenotypes, proteomic and lung imaging and later BPD status and respiratory health at 1 and 2 years of corrected age, and the development of prediction models for BPD using the early life respiratory endotypes.

EXPOSURES	
Eligible and enrolled infants will have clinical data relating to their antenatal, maternal and postnatal respiratory and neonatal intensive care course collected at pre-defined time points between birth and NICU discharge.
 
In addition, a maximum of 0.5 ml of blood will be collected at 72 hours and 7 days, and a brief LUS and EIT image of the lung performed at 48 and 72 hours, 7, 14 and 28 days, and then at 36 weeks' postmenstrual age (BPD diagnosis). Lung imaging and assessment of respiratory health using a standardised questionnaire will be repeated at 1 and 2 years corrected age in preterm survivors.

POTENTIAL CONFOUNDING FACTORS	
Maternal and antenatal factors and management, clinical decisions regarding respiratory support (site and clinician differences in guidelines and management), preterm non-respiratory complications (such as infection, neurological disease, necrotising enterocolitis, jaundice).

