3.1.2 Secondary objectives

The secondary objectives of this study are:

1. To compare the respiratory endotypes associated with different respiratory outcomes using observational data at 72 hours after birth in preterm infants born between 22+0 and 31+6 weeks' gestation.
2. To develop the first functional classification of preterm respiratory disease using a combination of clinical, lung imaging and molecular biomarkers.

3. Determine how specific early preterm endotypes relate to a diagnosis of BPD to develop a predictive modelling tool for the early diagnosis of BPD that can be used in everyday clinical practice.
4. Determine how specific early preterm endotypes relate to outcomes of the primary NICU admission, including duration of invasive mechanical ventilation and supplementary oxygen support, mortality, need for supplementary oxygen at discharge home.
5. To characterise the respiratory health of preterm infants in the first 2 years (corrected) after birth.
6. To characterise overall childhood health of preterm infants in the first 2 years (corrected) after birth.
7. To determine the relationship between initial respiratory endotype, BPD status and early childhood respiratory health at 1 and 2 years of corrected age.
8. To determine the performance of early life endotypes against a 36-week diagnosis of BPD in predicting respiratory outcomes at 1 and 2 years of corrected age.
9. To determine the relationship between LUS-derived measures of respiratory status at 14 and 28 days after birth and BPD status.
10. To determine the relationship between EIT-derived measures of respiratory status at 14 and 28 days after birth and BPD status.
11. To use plasma proteomics to identify proteins whose expression is altered in the first 7 days of life in infants who later are diagnosed with BPD.
12. To use plasma proteomics to identify expression pathways associated with specific preterm respiratory endotypes in samples obtained at 72 hours and 7 days post-birth.
13. To determine the impact of clinical interventions on the development of the respiratory phenotype.

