3.2 Outcomes

Table 3a defines the outcomes measures in relation to objectives and confounders.

Table 3a Listing objectives, exposure, outcomes and outcome measures, and confounders

PRIMARY OBJECTIVE
To comprehensively define the respiratory phenotype in the first 7 days after birth of preterm infants born between 22+0 and 31+6 weeks' gestation.

Exposure:
 
Day 7 after birth.

Outcome & outcome measure:
 
Functional endotypes defined from clinical, plasma protein and lung imaging measures using latent class analysis followed by external validation via group-based trajectory modelling.

Confounding factors:
 
Maternal and antenatal factors and management, clinical decisions regarding respiratory support (site and clinician differences in guidelines and management), preterm non-respiratory complications (such as infection, neurological disease, necrotising enterocolitis).

SECONDARY OBJECTIVES
To compare the respiratory endotypes associated with different respiratory outcomes using observational data at 72 hours after birth in preterm infants born between 22+0 and 31+6 weeks' gestation.

Outcome & outcome measure
 
Functional endotypes defined from clinical, plasma protein and lung imaging measures using latent class analysis (LCA) followed by external validation via group-based trajectory modelling.

To develop the first functional classification of preterm respiratory disease using a combination of clinical, lung imaging and molecular biomarkers.

Outcome & outcome measure
 
Temporally specific respiratory phenotypes derived from longitudinal latent class analysis of clinical, lung imaging and molecular biomarker data from all time points of the study.

To determine how specific early preterm phenotypes relate to a diagnosis of BPD and use this delineation to develop a predictive modelling tool for the early diagnosis of BPD.

Outcome & outcome measure

BPD status at 36 weeks' corrected PMA using Walsh Definition and Jensen Grade of Severity and functional endotypes determined above.
SECONDARY OBJECTIVES cont.
To determine how specific early preterm endotypes relate to outcomes of the primary NICU admission, including duration of invasive mechanical ventilation and supplementary oxygen support, mortality, need for supplementary oxygen at discharge home.
Outcome & outcome measure

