To use plasma proteomics of samples obtained at 72 hours and 7 days post-birth to identify pathways whose expression is associated with specific preterm respiratory endotypes.

Outcome & outcome measure
 
Bioinformatic analysis to determine increased association of endotype-associated proteins with specific pathways and biological processes.

To determine the impact of clinical interventions on the development of the respiratory phenotype.

Outcome & outcome measure
 
Sub-analysis will be performed to identify the impact of clinical interventions on plasma proteome composition using clustering methods, including hierarchal clustering, principal component analysis and k-means clustering and one-way analysis of variance (ANOVA).
 
Clinical interventions will include (but not limited to) surfactant administration, mode of support, ventilator settings, corticosteroid administration, blood transfusion and duration of invasive ventilation.

*Measures to define ventilation and aeration patterns using EIT and LUS are based upon existing guidelines.(23) Both technologies are likely to generate new outcome measures and scoring systems for global and regional ventilation, aeration and lung mechanics during the study period. These outcome measures may be added if 1) they can be extracted from raw imaging data acquired at Scheduled Assessments and 2) they have been considered valid measures in international standards.

Outcome measures are further detailed in Section 6.

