8.2 Data management

8.2.1 Data generation (source data)

In this study, the following types of data will be collected:

- Personal identifying information (names, dates of birth, contact details, postcode, URN/MRN).
- Sensitive information including health data relating to the antenatal and postnatal (NICU) period from both infant and mother.
- Respiratory and general health status at 1 and 2 years of age (including details of hospital and health care service presentations between initial NICU (birth) admission and 2 years).
- Plasma samples collected at 72 hours and 7 days.
- LUS and EIT imaging data as detailed in schedule of assessments table.

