11.2 Statistical Analysis Plan and Methods of Analysis

A separate Statistical Analysis Plan (SAP) will be developed by the Study Statistician(s) and SSC.

Defining the early life respiratory phenotypes: Proteome, lung imaging, clinical and demographic data will be combined to examine longitudinal alterations with ANOVA (multi-comparison), generalised additive models and post-hoc analysis using Perseus/R. Both supervised and unsupervised multivariate approaches including principal component analysis (PCA), Latent Class Analysis, hierarchical cluster analysis and partial least square discriminant analysis (PLS-DA) maybe used to assess i) which clinical/protein/imaging measures tend to cluster at each time-point, ii) how background changes in protein densities, functional imaging and cardiorespiratory measures relate to different clinical treatments. Significant correlations between candidate proteins, imaging, clinical and physiological markers will be identified with permutation tests with custom R scripts written by the Study Statistician(s) and multivariate visualisations (network maps) of important clinical-imaging-protein trait interactions (assessed with canonical correlation analysis) visualised. Phenotype discovery will target two broad sub-types: 1) known and novel disease-mechanisms and 2) outcome-based signatures.

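### Objective 12 tests plasma proteins and pathways against endotypes partly built from the same plasma proteins, so ordinary p-values and enrichment tests there have no valid null

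*Protocol*

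**What the plan says.** The synopsis gives the primary outcome as "identification of functional endotypes defined from clinical, plasma protein and lung imaging measures". Table 3a (section 3.2) repeats this in the primary-objective row (Day 7) and in the row for the 72-hour comparison: "Functional endotypes defined from clinical, plasma protein and lung imaging measures using latent class analysis". In both rows the proteins are therefore inputs to the classes.

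Objective 12 (section 3.1.2) reads: "To use plasma proteomics to identify expression pathways associated with specific preterm respiratory endotypes in samples obtained at 72 hours and 7 days post-birth". Its outcome measure in Table 3a is "Bioinformatic analysis to determine increased association of endotype-associated proteins with specific pathways and biological processes".

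Section 8.2.1 lists "Plasma samples collected at 72 hours and 7 days", and the schedule in Table 5a shows proteomic profiling at no other visit. There is no later plasma sample on which the association could be tested.

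Section 2.2 says that a phenotype implies no mechanism, while an endotype is defined by a distinct function or by pathobiological mechanisms.

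**The concern.** Latent class analysis chooses classes that separate its indicators. If an indicator is then compared between the fitted classes, the grouping is a function of the data being tested, and the usual null distribution does not apply. The problem extends to proteins that were not indicators but move with ones that were. Because co-regulated proteins move together, whole modules can be flagged, and the enrichment step then reports them as pathways.

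At stake is what objective 12 can show. It is the listed objective that links endotypes to biological pathways, so its result would naturally be read as support for a mechanism. A comparison that tends to return differing proteins even when no classes exist cannot give that support.

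**Working it through.** **Are safeguards stated elsewhere?**
- Table 3a says the classes are "followed by external validation via group-based trajectory modelling". That is a second modelling method, and no other cohort is named.
- Section 11.2 says "Significant correlations between candidate proteins, imaging, clinical and physiological markers will be identified with permutation tests". These tests concern correlations among markers, not protein-by-class contrasts.
- Cross-validation and bootstrapping in section 11.2 belong to the risk prediction models.
- No protein-free class model, held-out proteins or held-out infants are described for objective 12.

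**Inputs.** The protocol gives no figure for objective 12. N = 550 comes from section 11.1. The following are assumptions: 10, 20 or 200 proteins as class inputs, 10 clinical or imaging indicators, and a within-pathway correlation of 0 or 0.3. Non-input proteins numbered 180, 180 and 20 respectively. Pathways held 20 proteins (one held 30 in the 10-input runs).

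**Null model.** There are no classes. Each protein is √ρ·F + √(1−ρ)·Z, where F is a continuous normal factor for its pathway and Z is independent noise. The clinical and imaging variables are independent of the proteins.

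**Fit.** A two-class mixture with local independence was used, the continuous analogue of latent class analysis: f(x) = Σ_k π_k Π_j N(x_j; μ_kj, σ²_kj). Class number was judged by BIC = −2 log L + q ln N, with q = 2pK + K − 1 for p indicators and K classes. With 10 proteins and 10 other indicators, p = 20, so q = 81 for two classes and 40 for one. The second class must lower −2 log L by more than 41 × ln 550 = 41 × 6.310 = 258.7.

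**Tests.** Each protein was compared between the two fitted classes by Welch t-test. Proteins were selected by Benjamini-Hochberg at 5%, and each pathway was tested by the hypergeometric distribution with Bonferroni correction over pathways. These tests were run in every replicate, whether or not BIC preferred two classes.

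**Results.** There were 200 replicates per row, and 60 for the 200-input rows.

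| Protein inputs, ρ | BIC prefers 2 classes | Input proteins p<0.05 | Any pathway enriched | Non-input proteins p<0.05 | All proteins p<0.05, protein-free classes |
|---|---|---|---|---|---|
| 10, 0 | 0% | 59.6% | 79.5% | 4.9% | 5.0% |
| 20, 0 | 0% | 54.4% | 97.5% | 5.1% | 5.0% |
| 200, 0 | 0% | 30.1% | 1.7% | 5.0% | 5.1% |
| 10, 0.3 | 100% | 100% | 100% | 10.2% | 5.3% |
| 20, 0.3 | 100% | 100% | 100% | 5.0% | 5.1% |
| 200, 0.3 | 81.7% | 57.0% | 100% | 5.2% | 5.3% |

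In every row, at least one input protein passed Bonferroni in all runs.

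**Reading the table.**
- With ρ = 0.3, a local-independence model can represent the correlation only by splitting infants into classes, so BIC accepts classes that do not exist.
- With independent proteins BIC keeps one class. The excess in those rows exists only because two classes were imposed.
- In the 10- and 20-input runs all input proteins sit in one pathway, which helps enrichment. The 200-input run at ρ = 0.3 does not rely on this, since its inputs fill ten pathways.
- In the 10-input run at ρ = 0.3, 10 of the 180 non-input proteins share a pathway with the inputs. If the other 170 are flagged at 5%, the ten are flagged in (0.102 × 180 − 0.05 × 170)/10 = (18.36 − 8.5)/10 = 0.99 of cases. Leaving a protein out of the class model does not protect it if its pathway partners are in.

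**Other settings.** A second null simulation with 550 infants, scored at 5% false discovery rate, gave 31-44% of independent input proteins significant with two classes forced. With correlation 0.3 it gave 48-73%, and BIC preferred two classes in every run. Protein-free classes gave about 0%. A third, with 525 infants and equal-variance classes, gave lower shares: 19-55% for independent proteins and 30-33% with ten co-expression modules. The direction is stable; the size depends on the assumptions.

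**The case against.** The strongest reply is that the Table 3a row names no test, p-value or error rate and does not say how an endotype-associated protein is identified. Section 11.2 leaves methods open and defers to a separate SAP. Describing which proteins characterise each class, and annotating their pathways, is legitimate. That stands: the fault lies in inference, not in description. But the protocol itself fixes that proteins are class inputs and that the same samples are then examined, and the row's wording reads as a finding of association.

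Class-number selection also protects in part. With independent indicators BIC stops at one class and nothing is left to compare. It does not protect at correlation 0.3, and proteins grouped in pathways are unlikely to be independent. In that setting the co-regulation is real variation between infants; what is false is cutting it into classes.

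If only a small panel enters the class model, most tested proteins are non-inputs and are flagged near 5%. This narrows the protein-level effect, but pathway partners of the inputs remain affected.

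Three stronger readings are tempting, and the documents do not support them.
- A reader might infer that false pathways will always appear. With about 200 independent inputs they appeared in 1.7% of runs.
- A reader might infer that the endotype claim cannot fail. Section 2.2 also allows an endotype to rest on function, which lung imaging informs. Objectives 3, 4, 7 and 8 set the classes against BPD, NICU outcomes and 1- and 2-year respiratory health, none of which is a first-week input.
- A reader might extend the point to the ANOVA under objective 13. That row lists clustering methods and ANOVA side by side and does not say that ANOVA compares proteome-derived clusters.

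**Conclusion.** The point holds for inference under objective 12. Proteins that helped form the endotypes, or that are co-regulated with those proteins, cannot be tested against the endotypes with ordinary p-values or enrichment tests. In data without classes, a moderate within-pathway correlation was enough for BIC to accept two classes in 82-100% of runs. In the two simulations run at correlation 0.3, roughly half or more of the input proteins differed between the classes. The number of input proteins, the correlation and the Gaussian form are assumptions, and only one against two classes was compared.

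Objective 12 as written is therefore not independent evidence of mechanism. The reach is limited to this one secondary objective. The construction of the primary classes, the sample size and the BPD prediction model are not affected. Objective 11 is not affected either, because it compares proteins by BPD status, which is defined clinically. This should be corrected before analysis, but it does not threaten the study's main aim.

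**What to change.** In the objective 12 row of Table 3a and in section 11.2:
- Base inferential protein and pathway tests on classes fitted from clinical and imaging indicators only.
- Report the protein and pathway profiles of the three-domain endotypes as description, without p-values or enrichment claims.

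Splitting the infants is not a substitute if the test half is still assigned to classes using its own proteins.

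The cost is one extra latent class fit and some wording. The real downside is that protein-free classes may be coarser than the three-domain endotypes and are not identical to them, so the inferential question changes somewhat. The report should say so.

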4.2 Overall design

This is a prospective observational study involving infants born preterm who require care in a participating Victorian Level 6 NICU. The overall purpose is to generate a large dataset to robustly define the different early life preterm respiratory phenotypes, and then interrogate that dataset to determine the relationship between these phenotypes (and biomarkers used to define them) and later BPD and 1- and 2-year respiratory health status.

Infants born between 22+0 and 31+6 weeks' gestation who meet all inclusion (and no exclusion) criteria and provide prospective written informed parental/guardian consent will be included in this study. This gestational age (GA) range has been chosen to align with those included in the Australian and New Zealand Neonatal Network (ANZNN) database. The ANZNN database aims to capture all preterm infants born in Australia and New Zealand (opt out consent).

The BLUEPRINT study expects to enrol 550 infants over the course of the 3-year enrolment period across 5 tertiary level NICUs in Victoria.

Longitudinal observations and measurements will be taken from plasma proteins, LUS and EIT, in addition to a standardised set of clinical measured designed to reflect physiological status, delivered clinical care and known antenatal, maternal and postnatal respiratory outcome risk factors. All participating infants will receive standard NICU care as per the treating institution.

Eligible infants will be consented prospectively, and eligibility confirmed prior to study enrolment. Prior to blood sampling and lung imaging, the parents and/or legal representative of the infant will be reminded of their participation in the BLUEPRINT study. Prior to discharge, patient contact details will be confirmed by the study team for follow-up study timepoints. Post-discharge follow-up at 1 and 2 years of corrected gestational age is not mandatory but encouraged. Follow-up assessments will be completed at the MCRI ([name]).

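### The methods named for the impact of clinical interventions (clustering, PCA, one-way ANOVA) cannot adjust for gestation or other confounders of non-randomised treatment

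*Protocol*

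**What the plan says.** Objective 13 in Protocol section 3.1.2 reads: "To determine the impact of clinical interventions on the development of the respiratory phenotype". Its row in Table 3a (section 3.2) says: "Sub-analysis will be performed to identify the impact of clinical interventions on plasma proteome composition using clustering methods". The tools listed are hierarchical clustering, principal component analysis, "k-means clustering and one-way analysis of variance (ANOVA". The interventions include, without being limited to, "surfactant administration, mode of support, ventilator settings, corticosteroid administration, blood transfusion and duration of invasive ventilation".

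Treatment is not assigned by the study. Section 4.2 states: "All participating infants will receive standard NICU care as per the treating institution".

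On confounding, section 3.2 introduces the table with "Table 3a defines the outcomes measures in relation to objectives and confounders", but a confounder list appears only under the primary objective. That list covers maternal and antenatal factors, "clinical decisions regarding respiratory support (site and clinician differences in guidelines and management", and non-respiratory complications. The synopsis gives nearly the same list for the study as a whole. Neither list names gestation or baseline severity. Gestation appears elsewhere:

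- Section 9.2 calls gestational age and sex major determinants of respiratory status.
- Section 2.1, first specific purpose, promises to delineate how gestation, maternal factors and interventions each influence marker expression.

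**The concern.** The objective is worded causally, the exposures are chosen by clinicians, and the only inferential method in the row has a single factor. Where treatment choice depends on gestation, and a protein's level also depends on gestation, a one-way ANOVA across treatment groups shows a difference even if the treatment does nothing. Clustering and PCA have the same limit: infants of similar maturity can fall together, and treatment labels will then line up with the clusters.

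What is at stake is a list of proteins apparently altered by surfactant, steroids, transfusion or ventilation, in which effects of maturity cannot be told from effects of treatment. That would defeat the separation promised in section 2.1.

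The row also leaves the exposure window open. Plasma is taken only at 72 hours and Day 7 (section 6.2.5), while durations of invasive support are recorded through to discharge (section 6.2.8). The row does not say that exposure stops at the sample.

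**Working it through.** **1. Does the named method adjust?** One-way ANOVA has one factor and no covariates. Hierarchical clustering, k-means and PCA take the protein matrix and no covariates. So nothing in the row adjusts.

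**2. Is adjustment attached to this objective elsewhere?**

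| Place in protocol | What it offers | Tied to objective 13? |
|---|---|---|
| 2.1, first specific purpose | Aim to separate gestation from interventions | Aim only, no method |
| 11.1 | Stratification by gestation/weight, sex and early intubation | No; a property claimed for the BPD prediction sample size |
| 11.2 | Generalised additive models for longitudinal change | No covariate set, no link to interventions |
| 11.2 | PCA, latent class analysis, clustering and PLS-DA, which may be used to relate proteins to treatments | No adjustment stated |

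The protocol states the aim of separation but gives no method that achieves it.

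**3. How large could the bias be?** The plan has no figure to reproduce, and the strength of confounding is not in the documents. I therefore assumed ranges.

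Inputs:
- N = 550 infants (sections 1.3 and 4.2).
- Correlation r between protein and gestation: 0.1 to 0.5 (assumed).
- Odds ratio for treatment per SD lower gestation: 1.5, 2 or 3 (assumed; about half the infants treated).
- True treatment effect: zero. Two groups, two-sided 5% per protein, no multiplicity correction (assumed).
- 1,000 simulated studies per cell. One-way ANOVA was compared with a linear model containing treatment and gestation.

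False-positive rate of the one-way ANOVA, with the mean spurious standardised difference d in brackets:

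| r | OR 1.5 | OR 2 | OR 3 |
|---|---|---|---|
| 0.1 | 7.8% (0.04) | 11.6% (0.06) | 18.2% (0.09) |
| 0.2 | 14.0% (0.08) | 31.7% (0.12) | 57.0% (0.18) |
| 0.3 | 27.4% (0.11) | 57.6% (0.19) | 86.2% (0.27) |
| 0.5 | 63.5% (0.20) | 96.3% (0.32) | 99.8% (0.45) |

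With gestation in the model the rate is 4.2% to 6.0% in every cell. The 95% simulation margin around 5% is 1.96 × √(0.05 × 0.95 / 1000) ≈ 1.4 points, so this is compatible with the nominal level.

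**4. Closed-form check.** With groups of about equal size, SE(d) ≈ 2/√550 = 0.0853, z = d/SE, and the rejection probability is Φ(z − 1.96) + Φ(−z − 1.96).
- Mildest cell: d = 0.038, z = 0.45, giving 7.3% (simulated 7.8%).
- r = 0.2, OR 2: d = 0.124, z = 1.45, giving 30.7% (simulated 31.7%).
- r = 0.3, OR 2: d = 0.185, z = 2.17, giving 58.3% (simulated 57.6%).

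The two agree within simulation error.

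**The case against.** The strongest reply is that the row is an outcomes-table entry, labelled a sub-analysis, for the last of thirteen secondary objectives, and that most of its tools are descriptive. Section 11.2 uses associational wording on treatments, lists more flexible models and defers to a separate SAP, where covariate sets usually belong. This stands in part: the protocol leaves adjustment unstated rather than ruling it out. But the row does more than stay silent. It names a one-factor test for a question about impact, and a SAP that adjusted would have to depart from it.

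Several stronger readings are tempting but are not supported:

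- *Table 3a contradicts its own confounder list.* That list sits under the primary objective and does not name gestation or baseline severity. Its item on respiratory-support decisions also overlaps with the exposures of objective 13. The firmer grounds are sections 9.2 and 2.1 and the study-wide list in the synopsis.
- *Ventilation time after the sample will be counted.* The row does not say total duration, and section 6.2.3 collects type and duration of support over windows that match the sampling points. This is an unstated window, not an error.
- *Results will be reported as treatment effects.* That is an inference about future reporting.
- *The percentages estimate the bias in this study.* Correlations, odds ratios, group sizes and the uncorrected 5% threshold are all assumed, and the number of infants with usable plasma may be below 550. A smaller N or a multiplicity correction lowers the rejection rate but leaves the spurious difference in place.
- *Everything needed for adjustment is already collected.* Gestation, birth weight, sex and antenatal steroids are (section 6.2.3). Severity just before each exposure is not clearly available: surfactant is listed by use, type, delivery method and dose, and blood products by need, neither with timing.

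**Conclusion.** The point holds as a mismatch between question and method. Table 3a addresses the impact of non-randomised interventions on the plasma proteome with methods that cannot adjust, while the protocol elsewhere treats gestation as a major determinant and aims to separate it from interventions. The direction of the problem needs only that treatment choice and protein level both vary with gestation. Its size cannot be read from the documents. Over the assumed ranges, spurious differences run from 0.04 to 0.45 SD and false-positive rates from about 8% to over 99%, against about 5% after adjustment. In that simulation gestation is the only confounder, so the adjusted result shows what one covariate can do, not that adjustment removes confounding by indication. The plan should be changed, but the point touches one secondary objective and leaves the primary endotype analysis and the BPD prediction model alone.

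**What to change.** Amend the objective 13 row of Table 3a as follows:

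1. Replace the one-way ANOVA with a regression for each protein on the intervention, adjusted for at least gestation, birth weight, sex, antenatal steroids and site. Add early severity from data already listed in section 6.2.3, for example delivery-room FiO₂ and SpO₂/FiO₂. Regression also takes ventilator settings and duration of ventilation as continuous exposures, without cutting them into groups.
2. State that exposure, including duration of invasive ventilation, is counted only up to the 72-hour or Day 7 sample being analysed.
3. Keep clustering and PCA, labelled as descriptive.
4. Report results as associations and reword the objective to match, because residual confounding by indication will remain.

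The cost is a wording change and slightly more analysis work, with no new data needed for the core covariates. The limit is that adjustment for severity immediately before each exposure may not be possible where treatment timing is not recorded. The amended text should say so.
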